1.1 Research Project

Introvision in Migraine - IntroMig

Clinical Trials Number

NCT03507400

Proposers

Dr. med. [name]

Neurology Consultant

Ludwig-Maximilians University Munich

Department of Neurology

Hospital of the Ludwig-Maximilians-University (LMU) Munich - Großhadern

[name]

[name]

Telephone: [name]

E-mail: [contact]

Univ.-[name]. med. [name]

Senior Physician

Department of Neurology

Ludwig-Maximilians University Munich

Hospital of the Ludwig-Maximilians-University (LMU) Munich - Großhadern

[name]

[contact]

E-Mail: [contact]

Univ.-[name]. [name]

Pedagogic Psychology

Department of educational science

Research Group Introvision, University of Hamburg

[name]

[name]

[contact]

E-Mail: [contact]

Table of contents

1. Hypothesis
2. Study type
3. Study design and discussion of ethic-legal issues
4. Capability of informed consent
5. Compensation for subjects and patients, additional costs, insurance
6. Data protection

1. 1. Hypothesis

Is Introvision, a technique to reduce stress, effective in reducing the number of headache days per month in patients with episodic migraine (diagnosed according to IHS 3 beta), episodic migraine and episodic tension type headache or chronic migraine 3 months after Introvision (primary outcome measure) compared to the waiting list group. Secondary outcome measures are efficacy in reduction of headache intensity, acute medication, impact of headache (headache impact test -6; HIT-6) and patients' overall satisfaction with treatment. Do patients improve in headache self-efficacy, measured with the Headache Management Self-Efficacy Scale Short Form (HMSE-G-SF).

2. Study type

monozentric randomized waiting-list-control study (,investigator-driven').

3. 3. Study design and discussion of ethic-legal issues

Inclusion criteria:

1. minimum age is 18 years
2. episodic migraine (at least 5 headache days per month), episodic migraine and episodic tension type headache (at least 5 migraineous headache days) or chronic migraine (more than 15 headache days per month, out of which at least 8 migraineous headache days for three months), diagnosed according to IHS 3 beta.
3. stable headache-preventative medication
4. stable non-medication preventative measures (for instance regular sports)
5. written informed consent

Exclusion criteria:

1. other symptomatic headaches
2. other primary headaches (Cluster headache, trigeminal neuralgia, idiopathic facial pain, new daily persistent headache)
3. manifest severe depression (BDI-FS > 13 points)
4. drug- or alcohol abuse
5. non-compliance, especially missing entries in the headache diaries
6. active psychosis

For the study, the following data are collected:

- last name, first name, date of birth, age, sex of the patients
- number and intensity of headache days per month, documented in headache diary
- number of days with acute medication against headaches
- Beck-Depression-Inventory: Fast-Screen to document mood
- Headache Management Self-Efficacy Scale Short Form (HMSE-G-SF)
- number of KAW-exercises per week (0-1, 1-3, >3)
- patients' global satisfaction with treatment
- HIT-6 questionnaire (Headache-Impact-Test) to measure impact of headaches.

According to our previous experience with comparable study designs, we do not expect any lasting psychological stress for the subjects. There are no risks to the physical health of the subjects.

No additional investigations are needed for the study.

Due to the above-mentioned aspects no serious adverse events are to be expected. In case of serious adverse events both the director of the clinic as well as the ethics committee will be informed immediately.

4. 4. Ability to agree

The study includes only patients who can decide on their own to participate in the study. Only patients with a minimum age of 18 years will be included. Patients are informed in detail in writing and orally about aims and procedure of the study. The written information of the study as well as the form for the Declaration of consent are attached to this proposal.

5. 5. Remuneration of subjects and patients, additional costs, insurance

There is no remuneration for participants. Secondary costs due to additional diagnostics or a prolonged hospital stay are not to be expected.

[name] trains as certified instructor of Introvision, to be able to teach Introvision to study participants. There is no separate remuneration for the investigator, however, if a sponsor is found, an allowance (also for travelling expenses) is provided for the Introvision instructors as well as for the investigator. An enquiry for sponsorship will be sent to the Klaus-Grawe-Foundation, Zurich.

An insurance contract won't be effected, as in this research project no procedures with not very low risks for participants are planned. Study-related trips of the participants to the study are not insured. It is a therapy offer.

6. Data protection

The data protection of the participants is given highest priority: Only the most important personal data are collected (first name, last name, date of birth, age, sex). All collected data will be treated confidentially. They are stored or saved without a name or date of birth under a code number (pseudonymised). Material containing information about individual persons is locked and kept separate from the encoded data. Medical confidentiality and applicable data protection laws are respected. Data analysis is only be carried out by hospital staff, who are all subject to confidentiality. No individualized data will be passed on to a third party. Participants are informed about these procedure. The above mentioned points are explained in the patient information and in particular in the declaration of consent for data protection.

Dr. med. [name]

Neurology Consultant

[name]. med. [name]

Senior Physician of the Department of Neurology

[name]. [name]

Pedagogic psychology, Department of educational science

Research Group Introvision, University of Hamburg

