Sample size estimation Introvision Study for headache

Randomized comparison of Introvision vs. waiting group in relation to headache days after Introvision (approx. 5 months after the study was started) or at the time of entry into Intervention phase (Waiting list group)

Specifications: Comparison of average headache days per month at survey time between Introvision group (experimental group) and waiting list group (control) by means of T-test for independent samples

Values assumed:

Introvision group:

Mean value 6, 5.5, or 5 headache days per month, standard deviation: 4.5, 5, 6, 7 days

Control group:

Average 8.5 headache days per month, standard deviation: 4.5, 5, 6, 7 days

Difference (effect): 2.5, 3, 3.5 headache days per month, standard deviation: 4.5, 5, 6, 7 days

Statistical test: T-Test for independent samples (analysis also with Mann-Whitney-U-Test)

Significance level: 5% double-sided (maximum probability of having a significant result in the event of a lack of effect); statistical power 80% (minimum probability of detecting an actual effect in the assumed order of magnitude)), 1:1 randomization

Result of the sample size estimation: See table

| Medium effect (Headache days per month) | Standard deviation (Headache days per month) | Sample size group | Total sample size |
|---|--|-------------------|-------------------|
| 2.5 | 4.5 | 52 | 104 |
| 3 | 4.5 | 36 | 72 |
| 3.5 | 4.5 | 27 | 54 |
| 2.5 | 5 | 64 | 128 |
| 3 | 5 | 45 | 90 |
| 3.5 | 5 | 33 | 66 |
| 2.5 | 6 | 91 | 182 |
| 3 | 6 | 64 | 128 |
| 3.5 | 6 | 47 | 94 |
| 2.5 | 7 | 124 | 248 |
| 3 | 7 | 86 | 172 |
| 3.5 | 7 | 64 | 128 |

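### Episodic and chronic migraine are pooled with no stated stratification or adjustment for diagnosis, which costs precision and leaves the comparison open to chance imbalance

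*Protocol*

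**What the plan says.** Protocol section 3, inclusion criterion 2, admits "episodic migraine (at least 5 headache days per month"), the mixed form with episodic tension-type headache, "or chronic migraine (more than 15 headache days per month, out of which at least 8 migraineous headache days for three months"). The hypothesis in section 1 names all three groups in one pooled question about headache days. Section 2 calls the trial a "monozentric randomized waiting-list-control study" and says no more about allocation.

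The SAP specifies "Comparison of average headache days per month at survey time between Introvision group (experimental group) and waiting list group (control"), with "Statistical test: T-Test for independent samples (analysis also with Mann-Whitney-U-Test") and "Significance level: 5% double-sided". Its allocation statement is "1:1 randomization". The sample-size table covers effects of 2.5, 3 and 3.5 days and SDs of 4.5 to 7 days, giving 27 to 124 per group at 80% power, around a control mean of 8.5 days. It does not say which row was chosen.

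Neither document names strata, blocks, covariates or an analysis by diagnosis, and neither gives the expected share of chronic patients.

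**The concern.** Diagnosis is an entry criterion, so it is known for every patient before allocation. It also largely sets the expected value of the primary outcome: the two entry thresholds lie about 10 headache days apart, against a planned effect of 2.5–3.5 days. If diagnosis enters neither the allocation nor the analysis, two things follow.

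- The spread between diagnoses stays in the error term of the t-test, so the trial needs more patients than necessary for the same power.
- Any chance difference between the arms in the share of chronic patients passes straight into the estimated effect. A small chronic group may also split unevenly, leaving little randomised evidence in a population that the hypothesis names.

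**Working it through.** **Plan's own figures.** A two-sample t-test at two-sided 5% and 80% power reproduces all 12 rows within one patient per group. For effect 3 and SD 5, the normal formula 2(1.96 + 0.84)² × 5²/3² gives 43.6, and the noncentral t gives 44.6, so 45. For effect 3 and SD 6, the noncentral t gives 63.8, so 64.

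**Assumptions.** Let p be the chronic share and D the chronic-minus-episodic gap in mean headache days at follow-up. Neither is in the documents. I take p = 10–20% and D = 8–10 days, with the same treatment effect in both diagnoses. Two checks:

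- *Control mean.* With 8.5 days overall, the episodic mean is 8.5 − pD, which is 6.5 to 7.7 days, and the chronic mean is D higher, 14.9 to 17.5 days. That is close to the entry thresholds.
- *SD.* The between-diagnosis SD is D√(p(1 − p)), which is 2.4 to 4.0 days. It fits inside every SD in the SAP.

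**Chance imbalance.** With n per arm, the SD of the shift in the arm difference is D√(2p(1 − p)/n). At n = 45 and an effect of 3 days:

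| p | D | 1-SD shift (days) | share of 3 days | chance of ≥1.5 days, either direction |
|---|---|---|---|---|
| 10% | 8 | 0.51 | 17% | 0.3% |
| 10% | 10 | 0.63 | 21% | 1.8% |
| 20% | 8 | 0.67 | 22% | 2.6% |
| 20% | 10 | 0.84 | 28% | 7.5% |

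The chance of a shift of 3 days or more is at most 0.04% in these four cases. For any p and D compatible with a row of the SAP table it is at most 0.5%.

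**Type I error.** With n = 45, SD 5, p = 20% and D = 10, simulation (20,000 trials) of the unadjusted t-test gives 4.9% false positives and 80% power, averaged over randomisations.

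**Power, with allocation and adjustment separated** (effect 3 days, 8,000 simulated trials per cell):

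| Allocation and analysis | 64 per arm, SD 6, p 20%, D 8 | 45 per arm, SD 5, p 10%, D 8 |
|---|---|---|
| simple, t-test | 80.6% | 80.7% |
| stratified, t-test | 84.1% | 83.2% |
| simple, stratum term | 91.3% | 89.1% |
| stratified, stratum term | 91.2% | 88.9% |

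A formula check agrees. The within-diagnosis SD is √(SD² − p(1 − p)D²). That is √(36 − 10.24) = 5.08 in the first setting and √(25 − 5.76) = 4.39 in the second, and the noncentral t then gives 91.3% and 89.4%.

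The gain depends on the inputs. At 124 per arm, effect 2.5, SD 7, p = 10% and D = 8, the within-diagnosis SD is √(49 − 5.76) = 6.58 and power is about 85%. At 45 per arm, effect 3, SD 5, p = 20% and D = 10, the within-diagnosis SD falls to √(25 − 16) = 3.0 and power exceeds 99%, which shows how strong that combination is.

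**Split within the chronic group.** With 11 chronic patients allocated by simple 1:1 randomisation, a split of 3 versus 8 or worse has probability 2 × (1 + 11 + 55 + 165)/2¹¹ = 464/2048, about 23%.

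**The case against.** The case for leaving the plan alone has several parts.

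- *The test is valid as it stands.* If the SD describes the mixed population, the t-test's variance already contains the spread between diagnoses. This stands. A reader might infer that imbalance biases the trial or inflates false positives. It does so only conditionally on an unlucky draw: with 45 per arm, SD 5, p = 20% and D = 10, a 1.96-SD imbalance gives about 26% false positives, but perfect balance gives about 0.1%, and the average is the nominal level.
- *Large shifts are rare.* This stands. A reader might infer that imbalance could readily imitate or cancel most of the planned effect; the table above shows that even half of it is a tail event. Nor can the size be pushed up with a 30% chronic share and an 11-day gap, because the between-diagnosis SD would be 11√0.21 = 5.04 days, more than the whole SD of 5 in the rows with 45 and 33 per group.
- *The power gain belongs to adjustment, not allocation.* This is largely right: with the stratum term in the model, stratified allocation adds nothing measurable to power.
- *The allocation method is not described.* This stands. That randomisation was unrestricted is an inference from silence; a stratified scheme may exist and be unwritten.
- *No analysis by diagnosis is planned, and 5 versus 6 chronic patients would still be a thin comparison.* This stands as to inference within that subgroup. Near-equal numbers remain worth having, because they also protect the planned unadjusted t-test and Mann-Whitney test.

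**Conclusion.** The point holds as one of efficiency and robustness, not of validity. The plan pools diagnoses that differ strongly on the outcome scale and states no use of diagnosis in allocation or analysis. Under the assumed 10–20% chronic share and 8–10 day gap, an ordinary imbalance at 45 per arm is worth about 0.5–0.8 days (17–28% of a 3-day effect). In the two simulated settings, ignoring diagnosis costs about 8 to 11 points of power. The cost is smaller where the SD is large and the chronic group small, and larger where the gap explains most of the SD.

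These sizes rest on a chronic share and a gap that the sponsor would have to supply, on the gap persisting to follow-up, and on a common treatment effect. If baseline headache days are adjusted for, much of the same variation is removed, so the two gains overlap and must not be added.

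**What to change.** In the SAP, replace the bare allocation ratio with 1:1 randomisation in permuted blocks, stratified by diagnosis: episodic migraine with or without episodic tension-type headache, versus chronic migraine. Include the stratum as a term in the primary comparison; stratifying and then running the unadjusted t-test would leave most of the precision unused. State the expected chronic share and the SD it implies for the mixed population. Report the arm difference within each diagnosis descriptively. If a stratified scheme is already in use, it only needs to be written down, together with the matching model term.

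The cost is two allocation lists instead of one, slightly more administration at a single centre, and one model term. No extra patients, visits or data are needed. The allocation part has to be settled before the first patient is randomised; the stratum term should be fixed before outcome data are seen.

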Sample size estimation Introvision Study for headache

Randomized comparison of Introvision vs. waiting group in relation to headache days after Introvision (approx. 5 months after the study was started) or at the time of entry into Intervention phase (Waiting list group)

Specifications: Comparison of average headache days per month at survey time between Introvision group (experimental group) and waiting list group (control) by means of T-test for independent samples

Values assumed:

Introvision group:

Mean value 6, 5.5, or 5 headache days per month, standard deviation: 4.5, 5, 6, 7 days

Control group:

Average 8.5 headache days per month, standard deviation: 4.5, 5, 6, 7 days

Difference (effect): 2.5, 3, 3.5 headache days per month, standard deviation: 4.5, 5, 6, 7 days

Statistical test: T-Test for independent samples (analysis also with Mann-Whitney-U-Test)

Significance level: 5% double-sided (maximum probability of having a significant result in the event of a lack of effect); statistical power 80% (minimum probability of detecting an actual effect in the assumed order of magnitude)), 1:1 randomization

Result of the sample size estimation: See table

| Medium effect (Headache days per month) | Standard deviation (Headache days per month) | Sample size group | Total sample size |
|---|--|-------------------|-------------------|
| 2.5 | 4.5 | 52 | 104 |
| 3 | 4.5 | 36 | 72 |
| 3.5 | 4.5 | 27 | 54 |
| 2.5 | 5 | 64 | 128 |
| 3 | 5 | 45 | 90 |
| 3.5 | 5 | 33 | 66 |
| 2.5 | 6 | 91 | 182 |
| 3 | 6 | 64 | 128 |
| 3.5 | 6 | 47 | 94 |
| 2.5 | 7 | 124 | 248 |
| 3 | 7 | 86 | 172 |
| 3.5 | 7 | 64 | 128 |

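### The only analysis named is an unadjusted t-test (with Mann-Whitney) at follow-up; adjusting for baseline headache days would add precision at almost no cost

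*SAP*

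**What the plan says.** The SAP is a single sample size estimation. Under Specifications it sets out the comparison: "Comparison of average headache days per month at survey time between Introvision group (experimental group) and waiting list group (control) by means of T-test", in the two-sample form. Its statistical test line reads "T-Test for independent samples (analysis also with Mann-Whitney-U-Test", and the error rate is given as "Significance level: 5% double-sided". The Protocol names no statistical test. Neither document mentions a covariate, change from baseline, a regression model or stratification.

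A pre-treatment value of the same outcome is nevertheless needed for entry. Inclusion criterion 2 (Protocol, section 3) asks for "episodic migraine (at least 5 headache days per month", or for "chronic migraine (more than 15 headache days per month" with a further condition on migrainous days over three months. The list of data collected in the same section includes "number and intensity of headache days per month, documented in headache diary". Exclusion criterion 5 is "non-compliance, especially missing entries in the headache diaries".

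The documents give no assessment schedule. That the diary count is taken before randomisation is therefore an inference. The eligibility rule and the diary exclusion are consistent with it but do not prove it.

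**The concern.** The entry criteria admit patients with as few as 5 headache days a month alongside patients with more than 15. Someone who starts high is likely to finish high whichever arm they are in. That is a reasoned expectation, not a figure in the documents. An unadjusted comparison leaves all of this between-patient spread in the error term. The SAP's SDs (4.5 to 7 days) are already large against its target effects (2.5 to 3.5 days).

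Two things are at stake. The first is precision: if baseline predicts follow-up, adjustment gives a narrower interval and more power from the same patients. The second is chance imbalance: if one arm happens to start with more headache days, about r times that difference passes into the unadjusted follow-up comparison, whereas an adjusted analysis removes it.

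**Working it through.** **Inputs.** From the SAP: two-sided 5% level, 80% power, 1:1 allocation, effects of 2.5, 3 and 3.5 days, SDs of 4.5, 5, 6 and 7 days, and the tabulated n per group. Assumed: r, the within-arm correlation of baseline with follow-up headache days, over 0.3 to 0.7.

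**Step 1: reproduce the table.** The noncentral-t solution for a two-sample t-test, in the SAP's row order and before rounding, is 51.84, 36.31, 26.94, 63.77, 44.59, 33.02, 91.39, 63.77, 47.11, 124.04, 86.44 and 63.77 per group. Rounded to the nearest integer, these match all 12 tabulated values. Power at the tabulated n is 79.7–80.4%. The table is correct for the test it names.

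**Step 2: precision with baseline adjustment.** ANCOVA replaces the SD by a residual SD:

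residual SD = SD × √(1 − r²)

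The standard error is multiplied by 0.954, 0.866 or 0.714 at r = 0.3, 0.5 or 0.7. The n needed for equal power is multiplied by 1 − r² = 0.91, 0.75 or 0.51.

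For the row with effect 3, SD 5 and 45 per group, the unadjusted standard error is 5 × √(2/45) = 1.054 days. The 95% half-width is 1.987 × 1.054 = 2.09 days. With adjustment:

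| r | Residual SD (days) | 95% CI half-width (days) | Power at 45 per group | n per group for 80% power |
|---|---|---|---|---|
| unadjusted | 5.00 | 2.09 | 80.4% | 45 |
| 0.3 | 4.77 | 2.00 | 83.9% | 41 |
| 0.4 | 4.58 | 1.92 | 86.7% | 38 |
| 0.5 | 4.33 | 1.81 | 90.2% | 34 |
| 0.6 | 4.00 | 1.68 | 94.0% | 29 |
| 0.7 | 3.57 | 1.50 | 97.6% | 24 |

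Deducting the covariate's degree of freedom changes these powers by about 0.01 percentage points. The result does not depend on the row chosen: over all 12 rows, power at the tabulated n is 83–84% at r = 0.3, about 90% at 0.5 and 97–98% at 0.7.

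**Step 3: check by simulation.** With 40,000 bivariate normal trials per setting (effect 3, SD 5, 45 per group), ANCOVA power was 83.1%, 90.0% and 97.4% at r = 0.3, 0.5 and 0.7. The formula is slightly optimistic because it ignores the small cost of estimating the covariate slope. At r = 0, ANCOVA gave 79.9% against 80.4% for the t-test. The t-test's type I error was 4.9–5.2%.

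**Step 4: chance baseline difference.** If the baseline SD equals the tabulated SD (a second assumption), the difference in baseline means has SD = SD × √(2/n). The smallest value over the 12 rows is 4.5 × √(2/52) = 0.88 days and the largest is 6 × √(2/47) = 1.24 days. About r times this carries into the unadjusted estimate:

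| r | Carried over (SD, days) | Share of the row's target effect |
|---|---|---|
| 0.3 | 0.26–0.37 | about 11% |
| 0.5 | 0.44–0.62 | about 18% |
| 0.7 | 0.62–0.87 | about 25% |

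In the same simulation the slope of the unadjusted difference on the baseline difference was 0.30, 0.50 and 0.70 at the three values of r, as expected.

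**The case against.** The strongest reply is that nothing here is wrong. The t-test is unbiased, keeps its 5% level, and has the power the table was built for. The SAP is headed as a sample size estimation, so its t-test could be read as a sizing assumption. Against that reading, the same line says "Statistical test: T-Test for independent samples (analysis also with Mann-Whitney-U-Test", which describes an intended analysis, and neither document contains any other.

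The size of the gain rests on an unknown r. Between r = 0.3 and 0.7 the saving in n runs from 9% to 49%, and at r = 0 adjustment is very slightly worse. This stands, and it is why a range is given. The imbalance figures also assume equal SDs at both times, which the floor of 5 days at entry may upset.

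The calculations assume normal data, yet the SAP's own values would put 9–24% of a normal Introvision group below zero days, from Φ(−6/4.5) to Φ(−5/7). The outcome is a bounded, probably skewed count. In one skewed simulation (gamma shapes assumed; means 8.5 and 5.5, SD 5, 45 per group), Mann-Whitney had about 93% power. ANCOVA had 84%, 91% and 98% at r of about 0.32, 0.51 and 0.72. So the gain is shown against the t-test, not always against the SAP's second test. However, Mann-Whitney does not estimate the difference in mean days on which the trial is sized, and ANCOVA still beat the t-test in those settings.

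Finally, if eligibility is judged from history rather than a diary, a diary period before randomisation would have to be added. That also stands.

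**Conclusion.** The point holds as a recommended improvement. The one named analysis ignores a pre-treatment measure of the primary outcome that eligibility already requires, and so gives up precision in estimating the mean difference. It causes no bias, no inflation of type I error and no fault in the sample size table.

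In the row worked above, the interval would be narrower by about 5%, 13% or 29% at r = 0.3, 0.5 or 0.7 (1 − 0.954, 1 − 0.866, 1 − 0.714), with the power gains tabulated. The direction holds for any correlation that is not close to zero. The size rests on the assumed r and on approximately normal data, and the use of the count rests on its being recorded before randomisation.

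**What to change.** - Name as primary analysis an ANCOVA of headache days per month at the primary time point on randomised group, with baseline headache days per month as covariate. Report the adjusted mean difference with its 95% CI.
- Keep the t-test and the Mann-Whitney test as sensitivity analyses. The latter also guards against skewed counts.
- State that the baseline diary count is recorded before randomisation.
- Adjust secondary outcomes in the same way wherever a baseline value is recorded.
- Fix the covariate in advance, so that adjustment is not chosen after any imbalance is seen.

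The cost is a change of SAP wording, one degree of freedom, and about half a percentage point of power if r were 0. The planned sample size need not change. If the baseline diary count is not already collected before randomisation, collecting it is an additional cost.

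### The primary t-test uses one value per patient at survey time, so patients without that value drop out and any earlier post-randomisation diary months go unused

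*SAP*

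**What the plan says.** The SAP is a short sample size note, and its Specifications contain the only statement of the primary analysis: "Comparison of average headache days per month at survey time between Introvision group (experimental group) and waiting list group (control"), by an independent-samples t-test, with a Mann-Whitney test alongside. Survey time is about 5 months after study start in the Introvision arm and entry into the intervention phase in the waiting-list arm. The protocol's Hypothesis section places the primary outcome "3 months after Introvision (primary outcome measure) compared to the waiting list group".

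The data come from a diary. Protocol section 3 lists "number and intensity of headache days per month, documented in headache diary". It does not say in which months the diary is kept.

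Neither document has a longitudinal model, a method for missing diary data or an allowance for loss. Gaps in the diary appear once, under non-compliance in the exclusion criteria (item 5). The text does not say whether that criterion still applies after randomisation.

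**The concern.** A two-sample t-test needs the survey-time value. A patient who stops the diary earlier has none, and the plan names no substitute, so that patient leaves the comparison. Any months recorded before stopping leave with the patient.

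This matters more than usual in this design. Patients know whether they are waiting or being treated, and they record the outcome themselves. Patients with many headaches may give up while waiting, or may abandon a training that does not seem to help. If that happens more in one arm, the patients remaining at survey time are no longer comparable. Loss of badly affected waiting patients understates the benefit; loss of badly affected Introvision patients overstates it and can produce a benefit where there is none. Earlier diary months, where they exist, carry the information needed to correct for this.

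**Working it through.** **Inputs from the SAP.** "Significance level: 5% double-sided", "statistical power 80"%, "1:1 randomization", "Average 8.5 headache days per month" in the control group, and "Difference (effect): 2.5, 3, 3.5 headache days per month, standard deviation: 4.5, 5, 6, 7 days". No planning case is singled out; the row with effect 3, SD 5 and 45 per group is used here.

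**Assumptions not in the documents.** Normal data; three post-randomisation monthly counts, the third being the survey value; equal correlation ρ of 0.5 to 0.8 between months; 20% loss after the first month; odds of leaving that double per SD of the first month's count (measured from the arm mean).

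**1. The SAP's own figure.** The normal approximation gives n = 2(1.96 + 0.842)² × (5/3)² = 2 × 7.85 × 2.78 = 43.6, so 44 per group. The noncentral t calculation gives 45, as stated. Across the 12 rows, the t calculation matches exactly in 6 and gives one more per group in the other 6, where power at the stated n is 79.7% to 80.0%. The table is sound for one value per patient with complete data. It has no term for loss: with a random 20% lost from each arm (36 per arm), power is 71%.

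**2. Bias from loss in one arm.** Let z be the standardised first-month count and p(z) the chance of leaving, with logit p = a + ln(2)·z. Setting the mean of p to 0.20 gives a = −1.52 and a mean of p(1 − p) of 0.149. For normal z,

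mean of z among those who stay = −ln(2) × 0.149 / 0.80 = −0.129.

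The survey-time mean of those who stay is therefore too low by ρ × 5 × 0.129:

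- ρ = 0.5: 0.32 days
- ρ = 0.8: 0.52 days

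With waiting-arm loss the t-test estimates 3 − 0.32 = 2.68 to 3 − 0.52 = 2.48 days. With Introvision-arm loss it estimates 3.32 to 3.52 days. With no true effect, Introvision-arm loss gives a false benefit of 0.32 to 0.52 days.

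**3. Simulation check** (6,000 runs per cell, ρ = 0.5, 0.7 and 0.8). The likelihood estimate regresses the survey value on the first month within arm and evaluates it at the first-month mean of everyone randomised.

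| True effect 3 days | t-test: estimate; power | Likelihood: estimate; power |
|---|---|---|
| Loss in waiting arm only | 2.5 to 2.7; 59–67% | 3.0; 77–78% |
| Loss in Introvision arm only | 3.3 to 3.5; 84–89% (raised by the bias) | 3.0; 76–78% |
| Same loss in both arms | 3.0; 71–72% | 3.0; 72–76% |
| No loss | 3.0; about 80% | 3.0; about 80% |

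The largest simulated bias is 0.55 days, so the range is put at about 0.3 to 0.6. With no true effect and loss in one arm, the t-test rejects in about 6% to 8% of runs and the likelihood analysis in about 5%.

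**4. Loss in both arms.** When the mechanism acts equally around each arm's own mean, the two shifts cancel. If it acts on the absolute count, loss falls to about 14% in the Introvision arm, whose mean is 3/5 = 0.6 SD lower. The t-test then estimates about 2.86 to 2.91, a bias of about 0.1 days.

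**5. Scale.** With 36 and 45 patients the standard error is 5 × √(1/36 + 1/45) = 1.12 days. The one-arm bias is thus roughly 0.3 to 0.5 standard errors, or 10% to 20% of the assumed 3-day effect.

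**The case against.** The strongest reply is that a t-test at one time point is a valid answer to the stated question when data are complete, and that the sample size table is right for it. That stands: with no loss, a repeated-measures contrast at the survey month gives the same estimate and the same power.

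It also stands that the size rests on assumed loss. One-arm loss is the unfavourable pattern; with similar loss in both arms the bias nearly vanishes and the gain is small. Nothing in the documents shows that loss will be large or unequal.

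The SAP does not state in words that patients without the value are excluded. That is fair, but the named test cannot include them and no alternative is given. The diary's monthly coverage is not stated either, so the remedy must be conditional on it.

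A reader might go further and infer that the outcome is a single month's count, and that its month-to-month noise wastes power even with full follow-up. The documents do not support this. The averaging window is undefined, so the value may be one month or several. The noise argument would justify averaging over months, but that changes the time point the protocol targets and can dilute an effect that builds up. The protocol's three-month wording for chronic migraine is part of a diagnostic criterion and says nothing about how noisy one month is.

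**Conclusion.** The point holds as one about missing survey-time values. The planned test discards patients who lack that value, together with any earlier months they recorded. Under the assumptions above, the cost is a bias of about 0.3 to 0.6 days when loss is confined to one arm, in either direction. It is close to nothing, apart from about 1 to 5 points of power, when loss is similar in both arms, and nothing when there is no loss. Confidence is moderate, because loss rate, correlation and diary schedule are all absent from the documents. The change is still worth making before unblinded data are seen: the direction of any bias cannot be known in advance, and the replacement estimates the same quantity.

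**What to change.** In the SAP Specifications, provided the diary is kept monthly from randomisation to survey time:

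- Make the primary analysis a repeated-measures model of all post-randomisation monthly headache-day counts, with arm, month and arm-by-month terms and an unstructured covariance.
- Include every randomised patient with at least one such month.
- Take the arm difference at the survey month as the primary contrast.
- Keep the t-test and Mann-Whitney test on the survey-time value as sensitivity analyses.
- State which diary month forms the survey-time value in each arm.
- State that the exclusion criterion on diary gaps does not remove randomised patients from this analysis.

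The cost is SAP wording and a little more analysis. No extra patients are needed, and no new data if the diary already runs throughout; if it does not, the schedule would have to be set first. The main downside is that the model assumes loss depends only on recorded counts. That is weaker than what the complete-case t-test needs, but it cannot be verified from the data.
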